### **9.3.3 Outcome measures**

Potential cases of hypothyroidism will be defined by:

- A coded diagnosis of hypothyroidism and/or
- A thyroid function tests indicating hypothyroidism and/or
- New use of thyroid replacement therapy

Cases of hypothyroid will be identified using ICD 9 DM codes, lab values and NDC codes. See appendix for code lists. From the exposed population we will identify all children who have a diagnosis of hypothyroidism in the 365 days after iodine contrast exposure. We will also identify those with lab values for low thyroid (TSH > 5.0 mU/L) or receipt of thyroid

replacement therapy in the 365 days post exposure. All children who meet any of these criteria will be considered potential cases of hypothyroidism. We will review the electronic record of each child considered to be a potential case to confirm that they did not have hypothyroidism prior to exposure to the iodine contrast agent. We will also look for codes that support the presence of the hypothyroid condition. For example if a child receives more than one prescription for thyroid replacement, or has multiple labs with high TSH levels, or multiple codes for hypothyroidism these will be considered likely cases. We will then obtain original clinical notes to validate the diagnosis, by searching for evidence of pre-existing thyroid conditions. Specifically will look for a positive diagnosis of hypothyroid, lab results, repeated lab tests, notes of other medications associated with lowered thyroid (see appendix 3 for list of drugs), and of Hashimoto thyroiditis, radiation, surgical procedures (see appendix 3 for list of procedures), and congenital forms of hypothyroid.

After review of their electronic medical record, detected cases will be classified into:

- Probable iodine-induced hypothyroidism: no other cause than the previous iodine contrast medium exposure could be identified
- Possible alternative etiology: Known other diseases (e.g. Hashimoto thyroiditis) or treatments (e.g. radiotherapy, drug treatments such as TK inhibitors, interferons, amiodarone and others) which may cause hypothyroidism
- Not a hypothyroidism case: No evidence of hypothyroidism in the patient's medical record, e.g. coding error

Estimated incidence rates will be calculated for all hypothyroidism cases together, and separate for "possible iodine induced hypothyroidism" and "possible alternative etiology."

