#### **9.2.3 Study population**

The study population will be all patients who were under the age of 4 at some time during the years 2008 to 2015 in the US- based KPNC database who had a procedure with iodinated contrast agent. A preliminary search of the data identified around 2300 people under age 4 who had a procedure with iodinated contrast, by searching CPT and HCPCS codes. We will also require that all children in the study were members of KPNC for at least 3 months before the iodinated contrast exposure, except where the child is under 3 months of age at time of initial exposure, and 2 weeks after the exposure. From this population we will exclude all children who had a diagnosis of hypothyroid any time prior to the iodine contrast exposure. We will also exclude those with lab values for low thyroid (TSH > 5 mU/L for children) any time before the

exposure, and those with thyroid replacement therapy, Hashimoto thyroiditis, or congenital hypothyroidism any time prior to the exposure.

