### **9.3.2 Exposure**

Exposure will be identified through CPT codes for procedures that include iodinated contrast agent. The date the procedure was coded will be considered the date of exposure. The majority of these will be CT scans with contrast. We will also identify young children who had a left heart catheterization including cardio-angiography, ventriculography, and coronary angiography. Each child will be followed for up to 365 days after a qualifying exposure (the exposure window).

There will be no differentiation according to any specific brand of contrast agents, considering that there is general agreement that iodine induced hypothyroidism is considered a class-effect of all iodinated contrast agents and not restricted to specific agents

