## **9.8 Quality control**

At the BCDSP/BU epidemiologists will work closely with our KPNC collaborators to ensure correct clinical definitions and data integrity. All analyses will be performed by trained epidemiologists familiar with large electronic health databases. We have procedures for checking data to be sure that the data have been correctly identified and classified. That is, we will check the characteristics of the study population to be sure they meet the study criteria by reviewing a random sample of electronic case records (“profiles”). We will create cross tabulations to describe the characteristics (including age, sex, comorbidities) of the study population and compare the results to the limited available epidemiology literature of hypothyroidism in young children and exposure to iodine in US youth. We will do data checks to confirm that person time was correctly calculated, and we will review the full electronic patient record to validate cases of

hypothyroidism and we will also abstract information from the patients complete medical records to validate all cases.

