## **9.9 Limitations of the research methods**

There is access to original clinical records in the KPNC database, thus validation will be possible. However we may miss some children who had procedure using iodinated contrast if the procedures were not coded properly. It is also possible that some children will have undiagnosed hypothyroidism. These will also be missed in this study.

Although most members enroll through their employers, many are members of KPNC through MediCal (a low-income health insurance plan). Analysis of U.S. census data demonstrates that KPNC members are representative of the general population with regard to ethnicity and education and differ only slightly with regard to income, we tend to underrepresent the very rich and the very poor. Members are remarkably similar to the general population in terms of employment status, marital status, screening practices, and prevalence of medical conditions, when compared with population-based data from the California Behavioral Risk Factor Surveillance System.

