Section 5: Exposure definition and measurement	Yes	No	N/A	Page Number(s)
5.1 Does the protocol describe how exposure is defined and measured? (e.g. operational details for defining and categorising exposure)				9
5.2 Does the protocol discuss the validity of exposure measurement? (e.g. precision, accuracy, prospective ascertainment, exposure information recorded before the outcome occurred, use of validation sub-study)				11
5.3 Is exposure classified according to time windows? (e.g. current user, former user, non-use)				10
5.4 Is exposure classified based on biological mechanism of action and taking into account the pharmacokinetics and pharmacodynamics of the product?				7
5.5 Does the protocol specify whether a dose-dependent or duration-dependent response is measured?				

Comments:

--

Section 6: Endpoint definition and measurement	Yes	No	N/A	Page Number(s)
6.1 Does the protocol describe how the endpoints are defined and measured?				10-11
6.2 Does the protocol discuss the validity of endpoint measurement? (e.g. precision, accuracy, sensitivity, specificity, positive predictive value, prospective or retrospective ascertainment, use of validation sub-study)				11

Comments:

--

Section 7: Confounders and effect modifiers	Yes	No	N/A	Page Number(s)
7.1 Does the protocol address known confounders? (e.g. collection of data on known confounders, methods of controlling for known confounders)				11
7.2 Does the protocol address known effect modifiers? (e.g. collection of data on known effect modifiers, anticipated direction of effect)				11

Comments:

--

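### No planned step explicitly confirms that iodinated contrast was given, so falsely coded exposures can stay in the rate and enter the probable iodine-induced category

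*Combined protocol and SAP*

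**What the plan says.** **Exposure.** Section 9.3.2 states: "Exposure will be identified through CPT codes for procedures that include iodinated contrast agent". Its timing comes from the same source: "The date the procedure was coded will be considered the date of exposure". The expected cohort is also a code count (section 9.2.3): "A preliminary search of the data identified around 2300 people under age 4 who had a procedure with iodinated contrast, by searching CPT and HCPCS".

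**Case review.** Section 9.3.3 has the electronic record of each potential case reviewed "to confirm that they did not have hypothyroidism prior to exposure to the iodine contrast agent", together with a search for codes supporting the diagnosis. Then: "We will then obtain original clinical notes to validate the diagnosis, by searching for evidence of pre-existing thyroid conditions". The items sought are the diagnosis, single and repeated laboratory results, other drugs, Hashimoto thyroiditis, radiation, surgery and congenital disease. Contrast administration is not among them. The probable iodine-induced category is assigned by exclusion, when nothing but the earlier contrast exposure explains the case. Coding error is foreseen for the outcome but has no counterpart for the exposure.

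**General checks.** Section 9.6 promises a review of electronic records for data validity. Section 9.8 checks that the study population fits the criteria by "reviewing a random sample of electronic case records", and abstracts the complete records of cases to validate the hypothyroidism.

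**Limitations.** Section 9.9 considers one direction of exposure error: "we may miss some children who had procedure using iodinated contrast if the procedures were not coded properly".

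**Checklist.** In Annex 2, "5.2 Does the protocol discuss the validity of exposure measurement" is ticked Yes, with a reference to page 11.

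**The concern.** Two results depend on the exposure code being right. The first is the primary incidence rate: a child who was coded but received no contrast adds person-time and, in most instances, no event. The second is the causal category. It works by eliminating other explanations and takes the exposure as given, so an unexposed child with hypothyroidism of unknown cause meets it. Few cases may fall in that category, so one wrongly labelled child could matter.

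The planned description of time from contrast to diagnosis (sections 8.2 and 9.7) also starts from the coded date, which no listed item compares with a recorded administration date.

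Section 9.9 accepts that procedures may be coded wrongly but discusses only missed children. The same kind of error can bring unexposed children in, and that is the error which dilutes the rate.

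**Working it through.** There is no plan figure to reproduce. The 2300 is a feasibility count, and the documents give no PPV, background incidence or precision target. What follows is a sensitivity calculation.

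**Inputs**
- N = 2300 (sections 9.2.3 and 9.5), counted before the membership and prior-disease exclusions. Full 365-day follow-up is assumed, so N is about 2300 person-years.
- Incidence in the truly exposed, I: 1% (assumed), or 8.3% (the term-infant figure from the literature review cited in section 7).
- PPV of the exposure codes: 0.95, 0.90, 0.80 (assumed).
- Background incidence, B: 0, or 0.2% to 0.5% per year (assumed).

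**Formulas**
- Unexposed children in the cohort = N × (1 − PPV)
- Observed incidence = PPV × I + (1 − PPV) × B
- Unexposed cases open to the probable label, if no other cause is found = N × (1 − PPV) × B

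**Dilution at a true 10 per 1000**

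| PPV | Unexposed children | Observed per 1000, B = 0 | Observed per 1000, B = 0.2% to 0.5% | Unexposed cases, B = 0.2% to 0.5% |
|---|---|---|---|---|
| 0.95 | 115 | 9.5 | 9.6 to 9.75 | 0.23 to 0.58 |
| 0.90 | 230 | 9.0 | 9.2 to 9.5 | 0.46 to 1.15 |
| 0.80 | 460 | 8.0 | 8.4 to 9.0 | 0.92 to 2.30 |

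**Effect on the causal category.** At I = 1% and PPV = 0.80 there are 1840 × 0.01 = 18.4 exposed cases. Unexposed children then make up 0.92/19.32 = 5% to 2.30/20.7 = 11% of all cases. At I = 8.3% the largest share is 2.30/155.0 = 1.5%.

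**Random error for scale.** With 23 cases in 2300 person-years, the exact Poisson 95% CI is 6.3 to 15.0 per 1000, and every observed rate in the table lies inside it. With 191 cases (about 8.3%) the interval is 71.7 to 95.7. With B = 0, PPV 0.90 gives 74.7, inside; PPV 0.80 gives 66.4, outside.

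**Why screening cases alone is not the remedy.** Take I = 1%, PPV = 0.90, B = 0.5%. The code-defined cohort has 20.7 + 1.15 = 21.85 cases, or 9.5 per 1000. Dropping the 1.15 unexposed cases but keeping all person-time gives 20.7/2300 = 9.0, further from 10. Scaling the person-time as well gives 20.7/(0.90 × 2300) = 20.7/2070 = 10.0.

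**Could the planned sample see the problem?** The protocol gives no sample size. If 5% of children were miscoded and the procedure report were read, the chance of meeting at least one is 1 − 0.95^50 = 92% in a sample of 50 and 1 − 0.95^100 = 99% in a sample of 100.

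**The case against.** The strongest reply is that the plan does contain checks that could catch this. Receiving a procedure with contrast is one of the study criteria, section 9.8 checks a sample of records against those criteria, section 9.6 promises a validity review, and complete records are opened for every case. This stands far enough to rule out two stronger readings that a reader might infer: that exposure is never checked in any way, and that the chart review validates nothing but the diagnosis. The review also covers prior disease and alternative causes. Nor do the documents say that electronic profiles hold codes only, so it cannot be claimed that they are unable to show contrast. What remains is that none of these checks names contrast administration, gives a sample size, or states what follows when a child turns out to be miscoded.

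A second reply is that details may sit elsewhere. Section 9.6 points to a data management plan that is not part of the documents, and section 9.7 ends in a redaction. The point is therefore limited to the visible text.

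A third is that nothing shows false-positive coding to be common, and that the two harms partly offset each other: with background near zero the dilution is largest and the mislabelled cases almost vanish. That is correct, and it keeps the point modest.

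The checklist argument is only supporting. By the table of contents, page 11 is where section 9.4 begins. That section discusses the accuracy of discharge diagnoses and laboratory data, not of exposure codes. Page breaks are not visible in the text, however, and section 9.9 does touch on miscoded procedures, so the entry may be no more than a poor page reference.

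**Conclusion.** The point holds as a gap in specification. Exposure and its date come from codes, no listed step explicitly confirms that contrast was given, and the probable iodine-induced category presumes that it was. The dilution is downward provided background incidence is lower than incidence in the exposed. Its size cannot be determined from the documents: under the assumed PPVs of 95% to 80% and near-zero background it is 5% to 20% in relative terms. That is less than random error at about 23 cases, but not at a low PPV with many cases. The expected number of mislabelled cases is between a fraction of one and about two, which matters mainly if cases are few.

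A reader might infer that the primary rate is seriously biased. The documents do not support that, since they give no evidence on how often these codes are wrong. The case for acting is that the error would be systematic, would lower the estimate in a safety study, and would go unmeasured when the records needed to measure it are already to be opened.

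**What to change.** 1. **Section 9.3.3:** add to the case abstraction whether contrast administration is documented in the radiology or catheterisation report (yes / no / not documented), with the administration date. Require yes for the probable iodine-induced label.
2. **Primary rate:** keep it on the code-defined cohort, so that numerator and denominator are selected in the same way.
3. **Section 9.8:** have reviewers of the random sample already planned read the procedure report. State the sample size and report the overall PPV of the exposure codes with its confidence interval, by procedure type only if numbers allow.
4. **Section 9.7:** add a sensitivity rate, contrast-confirmed cases divided by (PPV × person-time). Treat not-documented records identically in the numerator and in the PPV. State the assumption that miscoded and truly exposed children have similar average follow-up.
5. **Section 9.9:** say that false-positive exposure codes are possible and would dilute the rate. Correct the page reference for checklist item 5.2 to match.

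The cost is a little extra abstraction time: one item and a date in charts already open, and one report per sampled child. The sensitivity rate will carry the uncertainty of the PPV, and some truly exposed cases with incomplete reports will not qualify for the probable label.

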## **9.7 Data analysis**

Incidence density rates will be calculated using person-time of follow up. Baseline characteristics of the cases with hypothyroidism and of the rest of the cohort as well as the time-relation between iodine contrast exposure and diagnosis of hypothyroidism will be described using descriptive statistics. This will be done for all hypothyroidism cases and separately for the “probable iodine induced” category and the “possible alternative etiology” category. In the “probable iodine induced” category we will further ascertain the duration of the hypothyroidism episode.

If sample size and number of hypothyroidism cases allows, joint associations between possible risk factors and hypothyroidism will be examined in a multivariate statistical model (e.g. age, sex, bodyweight, type of procedure)

CCI

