***Codes used to identify medications and procedures associated with hypothyroidism***

Drugs and procedures	ICD-9-CM, CPT and NDC	Data source
Irradiation to neck	92.2	KPNC data
Cranial irradiation		
Neurosurgery		
Craniopharyngioma tumors		
Down Syndrome		
Turner Syndrome		
Propylthiouracil		
Methimazole		
Carbimazole		
Lithium		
Carbamazepine		
Valproic acid		
Ethotoin		
Phenytoin		
Amiodarone		
Interferon		

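### Children with a listed alternative cause cannot be classed 'probable iodine-induced', yet they stay in that class's person-time and comparison group

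*Combined protocol and SAP*

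**What the plan says.** Section 9.3.3 sorts cases after record review. The first class is "Probable iodine-induced hypothyroidism: no other cause than the previous iodine contrast medium exposure could be identified". The second takes cases with "Known other diseases (e.g. Hashimoto thyroiditis) or treatments (e.g. radiotherapy, drug treatments such as TK inhibitors, interferons, amiodarone and others) which may cause hypothyroidism". The section then states: "Estimated incidence rates will be calculated for all hypothyroidism cases together, and separate for" the two classes. At that point it labels the iodine class 'possible' instead of 'probable'; I read this as the same class.

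Section 9.2.3 removes children with an earlier hypothyroid diagnosis or a TSH above 5 mU/L, and "those with thyroid replacement therapy, Hashimoto thyroiditis, or congenital hypothyroidism any time prior to the exposure". The Annex 3 table "Codes used to identify medications and procedures associated with hypothyroidism" lists further causes: neck and cranial irradiation, neurosurgery, craniopharyngioma, Down and Turner syndromes, antithyroid drugs, lithium, anticonvulsants, amiodarone and interferon. None of these is an entry exclusion.

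Section 9.7 gives one denominator rule: "Incidence density rates will be calculated using person-time of follow up". It describes "Baseline characteristics of the cases with hypothyroidism and of the rest of the cohort", and adds: "This will be done for all hypothyroidism cases and separately for the “probable iodine induced” category" and for the alternative class. Section 9.3.1 counts comorbidities and co-medications among the baseline characteristics. The primary objective in section 8.1 is the rate of all detected hypothyroidism in the 365 days after exposure.

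**The concern.** On the wording of 9.3.3, a disease or treatment that may cause hypothyroidism is enough to move a case out of the 'probable' class. No timing or attribution test is given. A child on an anticonvulsant who becomes hypothyroid days after contrast would be counted as a possible alternative etiology. That child can add person-time to the 'probable' rate but not a case. The same holds from the day a listed treatment starts during follow-up.

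Two results are exposed. The 'probable' rate would vary with the case mix of the scanned population even if the risk from iodine were constant, which makes it hard to carry to another population. The table of 'probable' cases against the rest of the cohort would also show listed comorbidities and co-medications as absent among cases. A reader could take that for low risk in those children, when the class definition produces it.

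**Working it through.** **Inputs.** The documents give about 2300 exposed children (section 9.5, a preliminary code count before exclusions) and follow-up of up to 365 days (section 9.3.2), so at most about 2300 person-years. They give no expected rate, no precision target and no prevalence of alternative causes, so there is no planned figure to reproduce. All values of f, b/r and case counts below are assumptions.

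**1. Which causes are affected.** Hashimoto thyroiditis and congenital hypothyroidism present before exposure are excluded and do not dilute the rate. The remaining Annex 3 causes, and the TK inhibitors named only in 9.3.3, are not excluded.

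**2. Denominator effect.** Let d be the number of 'probable' cases, T the cohort person-time and f the share of T in children with an identified cause that was not excluded.

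- Rate as planned: d/T
- Rate in children who can receive the label: d/((1 - f)T)
- Ratio of the second to the first: 1/(1 - f)

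| f (assumed) | 1% | 5% | 10% | 20% | 40% |
|---|---|---|---|---|---|
| 1/(1 - f) | 1.01 | 1.05 | 1.11 | 1.25 | 1.67 |

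**3. Scale against sampling error.** With an assumed d = 20 and T = 2300, the planned rate is 20/2.3 = 8.7 per 1000 person-years, exact Poisson 95% CI 5.3 to 13.4. On cause-free person-time it becomes 9.2, 9.7, 10.9 and 12.4 at f = 5%, 10%, 20% and 30%, all inside that interval. With d = 50 the planned rate is 21.7 (16.1 to 28.7); at f = 20% it becomes 27.2, inside, and at f = 30% it becomes 31.1, outside.

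**4. Net direction as an iodine-induced rate.** Hypothyroidism from a cause that nobody identified also enters the 'probable' class. If such cases arise at rate b and truly iodine-induced cases at rate r, the planned rate divided by r is (1 - f)(1 + b/r). This is below 1 only if b/r < f/(1 - f).

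- f = 10%, b/r = 0.25: 0.90 × 1.25 = 1.13, too high
- f = 20%, b/r = 0.10: 0.80 × 1.10 = 0.88, too low

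**5. Circularity.** The prevalence of an identified listed cause among 'probable' cases is 0% by definition. Suppose 20% of the 2300 children have one at baseline and there are 20 'probable' cases. The table would show 0/20 against 460/2280 (20.2%), Fisher p = 0.021, with no protective effect present. With 10% and 20 cases it would show 0/20 against 230/2280 (10.1%), p = 0.25. The p-values only show how striking the artefact could look, since the plan announces no test here.

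**6. Spill-over to other factors.** If f were 30% in catheterised children and 10% in children having CT, equal true rates would give a 'probable' rate ratio of 0.70/0.90 = 0.78 by type of procedure.

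**The case against.** The strongest reply is that a class-specific rate over full-cohort person-time is a valid quantity: how often an exposed child develops hypothyroidism with no other cause found. With one denominator the two class rates also add up to the all-case rate. Swapping the denominator would lose that property. This stands, and it is why the remedy should add a rate and leave the planned ones in place.

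Other points stand in part:

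- The all-case rate is the quantity in section 8.1 and does not depend on the classification.
- The class tables are descriptive. The optional multivariate model in 9.7 has overall hypothyroidism as its outcome, with age, sex, bodyweight and type of procedure as examples.
- Classification follows record review, so some case-level judgement may be intended. The wording that a factor may cause hypothyroidism nevertheless points to presence being enough.
- Cases are classified from clinical notes, whereas non-cases could be flagged only from codes. This limits how exact the added rate can be.
- Part of section 9.7 is redacted, so a restriction could exist there. The finding is about the visible text.

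A reader might infer that the 'probable' rate is simply biased low. The documents do not support that for a true iodine-induced rate: there is no unexposed comparator, unidentified causes push the other way, and the net direction depends on b/r and f, neither of which is given.

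**Conclusion.** The point holds as a limited one. Relative to children who can receive the label, the 'probable' rate is diluted by the factor (1 - f). The dilution follows from the definitions, provided that an identified listed cause always disqualifies a case. Its size is unknown because f is not given: from 1% at f = 1% to 40% at f = 40%. With few cases and moderate f it would lie within the sampling error, but it is systematic and the confidence interval does not cover it.

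The description is circular for class-defining comorbidities and co-medications. For age, sex, weight or procedure type it is distorted only as far as these correlate with a listed cause.

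Two wider readings should be resisted. A reader might infer that the primary result is affected; it is not, because the all-case rate ignores the classes. A reader might also infer that the risk-factor analysis as a whole is circular; the model in 9.7 is for overall hypothyroidism and is not circular as written.

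**What to change.** In sections 9.3.3 and 9.7:

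1. Keep the all-case and class-specific rates on the full cohort, so that they still add up.
2. Flag the alternative causes in 9.3.3 and Annex 3 from coded data in the whole cohort, by the same rule for cases and non-cases.
3. Add a 'probable' rate on person-time free of such a cause, censored on the date when one first appears.
4. Report the rate of any hypothyroidism in children with and without such a cause. With the flag from step 2, numerator and denominator follow one rule and no etiologic judgement is needed.
5. Describe 'probable' cases against non-cases without an alternative cause, or leave class-defining characteristics out of that comparison.
6. Use one name for the iodine class throughout.

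The cost is small. Comorbidities and co-medications are already planned in 9.3.1 and Annex 3 already lists most of the causes, although its code entries need completing and TK inhibitors need adding. The added rate has less person-time and a wider interval. Code-based flags will miss causes recorded only in notes, so some dilution will remain and should be stated as a limitation.
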